**Endoscopic versus percutaneous biliary drainage for resectable
pancreatic head cancer with hyperbilirubinemia and
impact on pancreaticoduodenectomy: A prospective cohort study**

26 February 2021

Protocol

Introduction

Currently, pancreatoduodenectomy is the only curative treatment for patients with periampullary malignant tumors, such as pancreatic adenocarcinoma, distal cholangiocarcinoma, and duodenal neoplasms. The use of preoperative biliary drain (BD) for all jaundiced patients eligible for pancreatoduodenectomy has been called into question by the results of several studies, including 1 multicenter randomized clinical trial (RCT) (1) as well as several retrospective studies (2–4) and meta-analyses (5,6), in which preoperative BD failed to demonstrate any reduction in postoperative complication rates. However, most authors agree that preoperative BD should be performed on patients presenting with cholangitis; on patients who have very high levels of bilirubin (some authors suggest above 15–17 ml/dl); on patients who have borderline resectable neoplasms requiring neoadjuvant therapy; or in centers where the waiting list for the surgical procedure is long (7,8). Effective, albeit temporary, resolution of malignant biliary obstruction can be achieved by either percutaneous BD or endoscopic drain, which in turn may be either endoscopic retrograde cholangiopancreatography (ERCP) or nasobiliary drain (9). The merits of selecting one method over the other for patients awaiting pancreatoduodenectomy remain controversial due to potential procedure-related or postoperative complications. Despite being the first preoperative BD method employed to treat preoperative jaundice, percutaneous BD has been overmatched by endoscopic drain. However, in the current literature, it is difficult to find reasons that justify this preference.

Aim of the work

The aim of this prospective study is to compare postoperative complications in patients who will undergo pancreatoduodenectomy after either percutaneous or endoscopic preoperative BD, to determine which method is preferable in the preoperative management of such patients.

Patients

Sixty patients with resectable pancreatic cancer with high total bilirubin level more than 10 mg/dl and symptomatic jaundice, as cholangitis, intense pruritis, coagulopathy, severe nausea or anorexia, admitted to Gastro-intestinal Surgery Unit, Faculty of Medicine, Alexandria University, Egypt. Those with metastatic or locally advanced disease and those unfit for major surgery and anesthesia will be excluded.

Methods

All patients will be subjected to the following:

- Thorough history taking as regards symptoms of obstructive jaundice: pain, pruritis, coagulopathy and nausea.
- Complete physical examination:
 - General examination for fitness of surgery i.e. vital signs, severity of jaundice, anemia, malnutrition and dehydration.
 - Local abdominal examination: abdominal distension,
- Investigations:
 - Laboratory:
 - Routine: complete blood picture, fasting blood sugar, urea and creatinine.
 - Liver functions: prothrombin time, albumin, bilirubin (total and direct)
 - Liver cell integrity: AST, ALT, alkaline phosphatase.
 - Tumor marker: CA 19.9
 - Viral hepatitis markers
 - Imaging:
 - Ultrasound abdomen: diameter of CBD, intrahepatic biliray dilatation, condition of the liver, liver metastasis, ascites.

- Computed tomography of the abdomen/pelvis with oral and intravenous contrast: site, length, number, enhancement pattern of the tumor, relation to superior mesenteric vessels.

Patients will be randomly subdivided into two equal groups:

- The first group (group A) will be managed by endoscopic retrograde cholangiopancreatography (ERCP), endoscopic sphincterotomy with insertion of plastic stent 10 Fr under general anesthesia.
- The second group (group B) will be managed by Percutaneous Trans-hepatic Drainage (PTD) by interventional radiologist under local anesthesia. Either external or internal-external drainage technique will be performed according to the preference of the interventional radiologist,

For each method, the technical and clinical success rates will be observed by the improvement of liver functions and decrease in bilirubin after drainage.

Within 2 weeks, each patient in each group will undergo Pancreaticoduodenectomy (whipple operation) with triple anastomosis. Intra-operatively, technical difficulties as well as culture sensitivity from the catheter or stent will be recorded.

Patients will be closely observed in the immediate and early post-operative period for the occurrence of potential complications and mortality:

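### The drainage-success criterion can be read as needing prothrombin time or albumin to improve as well as bilirubin to fall, so a working drain in a patient with normal values could count as a failure; the documents do not settle the reading

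*Protocol*

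**What the plan says.** The only criterion for drainage success in either document is one sentence in the protocol's Methods section: "clinical success rates will be observed by the improvement of liver functions and decrease in bilirubin after drainage". It covers technical and clinical success together.

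The laboratory list in the same section reads "Liver functions: prothrombin time, albumin, bilirubin (total and direct". The enzymes stand under a different label: "Liver cell integrity: AST, ALT, alkaline phosphatase".

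Entry, under Patients, calls for "high total bilirubin level more than 10 mg/dl and symptomatic jaundice", with the symptoms given "as cholangitis, intense pruritis, coagulopathy, severe nausea or anorexia". No albumin or prothrombin time limit is set.

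The SAP defines no success endpoint. It compares qualitative variables between drainage types by chi-squared, Fisher or Monte Carlo tests, and quantitative variables by an unadjusted Student t test.

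**The concern.** The sentence joins two conditions with the word and. Bilirubin is already on the list of liver functions, yet its fall is named again. The liver-function half therefore adds something only if it brings in prothrombin time or albumin; the enzymes cannot supply the extra content, because the protocol labels them differently.

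Bilirubin has room to fall in every patient, since entry requires a value above 10 mg/dl. The other two tests carry no such guarantee. Coagulopathy is one of several alternative symptoms, so a patient may enter for pruritus with prothrombin time and albumin both normal. If such a patient must show improvement in one of them, the result may be a failure however well bile drains.

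The success rate would then partly measure who was abnormal at entry. The protocol plans to report success for each method and wants to say which method is preferable, so a rate that mixes drainage with baseline status is poor evidence. Because the wording allows both readings, the choice could also be made after the data are seen.

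**Working it through.** The documents state no drainage success rate, so there is no figure of theirs to reproduce. The check has a textual part and an illustrative calculation.

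**The two readings side by side**

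| Patient after drainage | Each half adds something | Bilirubin fall is enough |
|---|---|---|
| Bilirubin falls; prothrombin time or albumin abnormal at entry and improves | success | success |
| Bilirubin falls; both normal at entry and unchanged | failure | success |
| Bilirubin does not fall | failure | failure |

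Only the second row differs. The entry criteria allow such a patient, and neither document says how to classify one.

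**Inputs**

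- 30 patients per arm: 60 patients in two equal groups (protocol, Patients and Methods).
- Two-sided 0.05 level, Pearson chi-squared test, or Fisher's exact test when expected counts are small (SAP).
- True share of working drains, w: 95% in one arm and 75% in the other. **Assumption.**
- Share of patients with room to improve in prothrombin time or albumin, q. **Assumption**, varied from 100% down to 40%.

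**Formula.** Under the stricter reading, counted success = w × q. This takes q to be equal in both arms and unrelated to whether the drain works, and takes every patient who has room to improve and a working drain to improve. The difference between arms is (0.95 − 0.75) × q = 0.20 × q. Power is the summed probability of all 30 v 30 tables that the SAP's tests would call significant.

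| q | Counted success | Difference (percentage points) | Power |
|---|---|---|---|
| 100% | 95% v 75% | 20 | 49% |
| 80% | 76% v 60% | 16 | 26% |
| 60% | 57% v 45% | 12 | 16% |
| 40% | 38% v 30% | 8 | 10% |

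The q = 100% row is also the result of the looser reading.

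**Patients who change category.** Per arm this is 30 × w × (1 − q). With w = 0.90, q = 80% gives 30 × 0.90 × 0.20 = 5.4 patients, q = 60% gives 10.8, and q = 40% gives 16.2. Over w from 0.80 to 0.95 and q from 80% to 40%, the range is 30 × 0.80 × 0.20 = 4.8 to 30 × 0.95 × 0.60 = 17.1, or about 5 to 17 of 30.

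**The case against.** The strongest reply is that the protocol contains no scoring rule. It says success will be observed through these changes, which may merely list what is watched. It gives no pass/fail rule, no requirement that every component improve, and no treatment of normal values. Bilirubin is on the list of liver functions and is raised in every patient at entry, so a fall in bilirubin is itself an improvement in a listed liver function. This stands. A reader might infer that the protocol requires prothrombin time and albumin to improve, and that it does score working drains as failures; the text does not say so. The finding is an unresolved ambiguity.

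Second, with no threshold stated, a value within the normal range can still move in a favourable direction. This also stands: the ceiling at q applies only if improvement means correcting an abnormal value.

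Third, the size is assumed throughout, and power is only 49% even when no patient is misclassified. Both are true. The table shows the direction and the mechanism, and nothing more.

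Fourth, the stated aim is postoperative complications. That limits the weight of the point. It does not remove it, because success rates for each method are a planned observation.

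A reader might also infer that prothrombin time would improve because coagulopathy was corrected before the procedure. The documents describe no such treatment, and under the stricter reading it could not turn a failed drain into a success, because bilirubin must fall too. That argument is not relied on here.

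Finally, the SAP's t test already allows a separate comparison of prothrombin time and albumin. That is so, but the test takes no account of pre-drainage values.

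**Conclusion.** The criterion admits two readings that classify the same patient differently, and neither document chooses between them. Under the reading in which both halves carry content, the success rate depends on baseline prothrombin time and albumin, and any true difference between methods shrinks in proportion to the share of patients with room to improve.

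How much it would shrink is unknown. The figures rest on assumed success rates, an assumed share q that is equal in both arms and independent of drain function, and the view that normal values cannot improve. The documents supply none of these.

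The point concerns a secondary outcome. The main comparison of postoperative complications is untouched. It is still worth settling before analysis, because leaving it open allows the definition to follow the data.

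**What to change.** Reword the success sentence in the protocol's Methods section so that clinical success is judged on total bilirubin relative to the patient's own pre-drainage value, and take prothrombin time and albumin out of the success rule. The size and timing of the bilirubin fall also need stating; that is a separate gap. Repeat the definition in the SAP, which has none.

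In the SAP, compare post-drainage prothrombin time and albumin between arms as separate variables, each by analysis of covariance with its pre-drainage value as covariate, in place of the unadjusted Student t test.

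The cost is one sentence in the protocol and a short addition to the SAP. The tests are already on the laboratory list, and the present criterion already implies that they are repeated after drainage. The downside is that the success rate no longer reflects recovery of the liver's synthetic function; that is reported separately through the two adjusted comparisons.

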**Endoscopic versus percutaneous biliary drainage for
resectable pancreatic head cancer with hyperbilirubinemia
and impact on pancreaticoduodenectomy: A prospective
cohort study**

Date 16 March 2021

Statistical analysis plan

The minimum sample size required was 49 patients at 0.3% prevalence, accepting 5% error at 80% power and 0.05 level of significance.

Statistical analysis was done using Statistical Package of Social Science Program (SPSS) version 20. (Chicago: SPSS Inc.).

The qualitative variables were summarized by frequency and percentage. Chi squared test was used to test for association between the type of drainage and the other qualitative variables. Monte Carlo test or fisher exact test were used if more than 20% of the cells had expected cell counts < 5 .

The quantitative variables were summarized by the mean and standard deviation. Student' test was used to compare between the two types of drainage as regards the quantitative variables. Paired t test was used to compare between the pre and post-operative changes in the mean values of the quantitative variables. Multivariate 5% level of significance was used.

All tests of association or tests of comparison were done at 0.05 level of significance (two tailed).

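### The SAP's 49 patients with 80% power is not supported for the two-group comparison that the study is meant to make

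*SAP*

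**What the plan says.** The SAP sizes the study in one sentence: "The minimum sample size required was 49 patients at 0.3% prevalence, accepting 5% error at 80% power and 0.05 level of significance". It does not say which event has the 0.3% prevalence, what the 5% is an error in, whether 49 is a total or a number per group, or which formula was used. The protocol gives no sample size reasoning.

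The design is comparative. The protocol's aim is "to compare postoperative complications in patients who will undergo pancreatoduodenectomy after either percutaneous or endoscopic preoperative BD". Its Patients section begins "Sixty patients with resectable pancreatic cancer with high total bilirubin level more than 10 mg/dl", and its Methods section adds "Patients will be randomly subdivided into two equal groups", which makes 30 per group. For the analysis, the SAP states "Chi squared test was used to test for association between the type of drainage and the other qualitative variables" and, for sparse tables, "Monte Carlo test or fisher exact test were used if more than 20% of the cells had expected cell counts < 5". On the significance level it states "All tests of association or tests of comparison were done at 0.05 level of significance (two tailed").

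**The concern.** Power for a two-group comparison needs an endpoint and two rates, or one rate and a difference. The SAP gives one rate and an undefined 5%, yet attaches 80% power to the result. Either the figure belongs to a calculation other than the planned comparison, or essential inputs were left out.

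The interpretation of the main result is at stake. A reader who accepts 80% power may take a non-significant difference in complications as evidence that the two drainage methods perform alike. The plan shows no difference for which that power holds.

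**Working it through.** **Inputs.** From the SAP: p = 0.003, d = 0.05, 80% power (z = 0.842), alpha 0.05 (z = 1.960 two-sided, 1.645 one-sided). From the protocol: 60 patients in two equal groups. Where a formula needs a second rate, I assume that the 5% is a difference and take 5.3%.

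**Trying to reproduce 49, two-sided.**

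- Precision, z²p(1−p)/d²: 1.960² × 0.003 × 0.997 / 0.0025 = 4.6. With (1.960 + 0.842)² in place of z²: 9.4.
- One-sample test, [zα√(p0q0) + zβ√(p1q1)]²/d²: (1.960 × 0.0547 + 0.842 × 0.2240)² / 0.0025 = 35.0.
- The same with continuity correction, (n/4)[1 + √(1 + 2/(nd))]²: 53.1.
- One-sample exact binomial: 56.
- One-sample arcsine, (zα + zβ)²/h² with h = 2 asin√0.053 − 2 asin√0.003 = 0.355: 62.3.
- Two-sample test, per group: arcsine 2 × 62.3 = 124.6; unpooled 167.0; pooled 169.7; continuity-corrected 207.8.

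None of these gives 49.

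**Routes that do come to about 49.**

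| Route | Result | What it adds to the SAP |
|---|---|---|
| One-sided one-sample test, 0.3% v 5.3%, continuity-corrected | 48.99 | one-sided; 5% read as a difference; one group |
| One-sided one-sample test, 0.3% v 5.3%, arcsine | 49.06 | the same |
| Precision at p = 3%, plus 10% | 44.7 × 1.1 = 49.2 | misprint; inflation; no power term; one group |
| Precision at p = 3.3% | 49.0 | different prevalence; no power term; one group |
| Two-sample 30% v 60%, continuity-corrected | 48.4 per group | misprint; unstated second rate; 98 patients in total |

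The first two rows use all four of the SAP's numbers, but they test one group against a fixed rate. The last row compares two groups, but it would need 2 × 49 = 98 patients against the 60 planned.

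**Power of the planned test.** I enumerated all outcomes with 30 per group, using Pearson chi-square and switching to Fisher's exact test when more than 20% of expected counts are below 5. The test is two-sided at 0.05 and all rates are assumed.

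| Rates | Power |
|---|---|
| 0.3% v 5.3% | 0.4% |
| 20% v 40% | 39% |
| 30% v 50% | 35% |
| 5% v 33% | 79% |
| 10% v 40% | 79% |
| 20% v 54% | 79% |
| 30% v 65% | 80% |
| 40% v 75% | 80% |

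The first row is so low because hardly any events occur. With none in one group, Fisher's p for five in the other is 2 × C(30,5)/C(60,5) = 0.052, so six are needed. At 5.3% the expected number is 30 × 0.053 = 1.6.

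**Smallest difference with 80% power.** Over lower rates from 5% to 50%, the gap needed runs from 28.4 to 35.2 points. From a lower rate of 0.3% it is 25.6 points. If only 49 in total were enrolled (24 and 25), the gap is about 30 to 40 points, and power for 30% v 65% falls to 69%.

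**Precision of the risk difference, 30 per group.** The Wald 95% half-width is 1.96√[(p1q1 + p2q2)/30]. With equal rates it is 23.2 points at 30%, 24.8 at 40% and 25.3 at 50%. For 10% v 40% it is 20.6 points.

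**The case against.** The best defence is that no arithmetic error has been proved. A one-sided, continuity-corrected one-sample test returns 48.99 from the SAP's own four numbers. The sizing sentence states no sidedness, and the two-tailed statement is made about the analysis tests. On this view the fault is under-reporting, and 60 patients exceed the stated minimum in any case. This stands in part: 49 cannot be called irreproducible, and the documents do not show which method the sponsor used. It does not rescue the power claim, because 80% would then describe a single group against a fixed rate. Exceeding a minimum set for a different question says nothing about the comparison.

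A second objection is that a two-group route exists, 30% v 60% with 49 per group. It needs both a misprint and a second rate that appears nowhere, and it would put 60 patients below the minimum. It is a good reason to ask whether 49 is a total or per group.

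Third, the 0.4% figure depends on a rate that may be a misprint and on an assumed comparator. That is fair: it shows what the reading that reaches 49 implies and does not estimate the trial's real power. The rates used elsewhere are also assumptions, which is why a range is given.

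Finally, since only wording changes, one could rank the matter lower. I do not, because this is the plan's only power statement.

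**Conclusion.** The sentence is wrong as written and must be fixed. At two-tailed 0.05 none of the standard formulas tried returns 49 from the stated inputs. The routes found to about 49 need unstated choices, and none shows 80% power for the planned comparison with 60 patients. Nothing elsewhere in the documents supplies an endpoint, second rate or difference.

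Under assumed lower rates of 5% to 50%, 60 patients give 80% power only for differences of about 28 to 35 points. A 20-point difference from 20% or 30% would be missed more often than found. This does not show that 60 is too few for every plausible effect, because the plan gives no expected complication rate to judge that by.

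**What to change.** Withdraw the sentence, or correct it by stating the endpoint, both assumed rates, the formula, the sidedness, whether 49 is a total or per group, and whether 0.3% is a misprint. If the sponsor confirms that 49 was meant per group, the planned 60 must be reconciled with it. Otherwise keep 60 and state what the design delivers, for example:

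> With 30 patients per group and the planned chi-square or Fisher test at two-sided 0.05, for assumed lower rates of 5% to 50%, 80% power requires a difference of about 28 to 35 percentage points (for example about 10% v 40% or 30% v 65%). Power is about 39% for 20% v 40% and 35% for 30% v 50%. The risk difference in postoperative complications will be reported with a 95% CI (expected half-width about 23 to 25 points if both groups have the same rate, between 30% and 50%). A non-significant p-value will not be read as equivalence.

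The sponsor should replace the illustrative rates with its own if it has them. The cost is SAP wording, with no extra patients and no change to the planned tests. The drawback is a less favourable power statement and, if the sentence is corrected and not withdrawn, a commitment to a named endpoint and assumed rates.

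### If bilirubin and liver tests are compared between arms as continuous values, the SAP's unadjusted t-test leaves the collected pre-drainage value unused; under random allocation the cost is precision only (low severity)

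*SAP*

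**What the plan says.** The SAP paragraph on quantitative variables has one rule for comparing the arms: "Student' test was used to compare between the two types of drainage as regards the quantitative variables". It names no variable, no sampling time and no covariate, and does not say whether the post value or the change is compared. A second rule covers within-patient comparisons: "Paired t test was used to compare between the pre and post-operative changes in the mean values of the quantitative variables". A short sentence then attaches the word multivariate to the 5% significance level, without naming a model, outcome or covariate.

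The Protocol's Methods section lists prothrombin time, albumin, total and direct bilirubin, AST, ALT and alkaline phosphatase among the investigations for all patients, ahead of the allocation step: "Patients will be randomly subdivided into two equal groups". After drainage, technical and clinical success is judged by "improvement of liver functions and decrease in bilirubin after drainage", with no day fixed. Surgery bounds the interval: "Within 2 weeks, each patient in each group will undergo Pancreaticoduodenectomy". The Patients section sets the number and an entry limit: "Sixty patients with resectable pancreatic cancer with high total bilirubin level more than 10 mg/dl". Under Aim of the work, the comparison of interest is postoperative complications.

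**The concern.** A bilirubin value after drainage depends in part on where the patient started. Where a baseline has been measured, a comparison that ignores it leaves explainable variance in the error term. With 30 per arm, precision is already limited.

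The open outcome form adds to this. A t-test on the post value and a t-test on the change both fit the SAP's wording, and they can differ widely in power. ANCOVA on the baseline settles the choice and uses the data already in hand.

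What is at stake is the precision of a supportive comparison of how well each technique relieves the obstruction. The success rates are qualitative, fall under the chi-squared or Fisher rule, and are not part of this point.

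**Working it through.** **Is an adjustment already planned?** The Student's test has no covariate. The paired test compares a patient with himself or herself, so it does not compare the arms. The multivariate sentence specifies nothing that could be run. No baseline adjustment is therefore planned.

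**Inputs.** From the documents: 60 patients in two equal groups, so 30 per arm, and two-sided 0.05. Assumed, because the documents give nothing: a true difference of 0.5 SD of the post value, the correlation r between baseline and post value, and k = baseline SD / post SD. The SAP has no power figure for a continuous outcome to reproduce; its sample size of 49 rests on a prevalence.

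**Method.** Write v for the variance factor relative to the post value. The noncentrality is 0.5 / √(2v/30), and power comes from the noncentral t distribution.

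- Post value: v = 1, noncentrality 0.5 × √15 = 1.936, 58 df, power 47.8%.
- ANCOVA: v = (1 − r²)(1 + 1/56), 57 df. The factor 1 + 1/56 = 1.0179 is the price of estimating the slope.
- Change score: v = 1 + k² − 2rk, 58 df.

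**ANCOVA against the post value**

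| r | v | Power | Equivalent n per arm (30/v) |
|---|---|---|---|
| 0 | 1.018 | 47.1% | 29.5 |
| 0.1 | 1.008 | 47.5% | 29.8 |
| 0.3 | 0.926 | 50.7% | 32.4 |
| 0.5 | 0.763 | 58.7% | 39.3 |
| 0.7 | 0.519 | 75.2% | 57.8 |

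**Effect of the entry limit on total bilirubin.** Admitting only values above 10 mg/dl truncates the baseline and tends to lower r. Suppose the limit removes the lowest 25% or 50% of a normal baseline. Its variance falls to u = 0.535 or 0.363 of the original, and r becomes r√u / √(1 − r² + r²u). The 0.5 SD difference is now taken in SDs of the post value in the admitted patients.

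| Unrestricted r | r after 25% / 50% removed | ANCOVA power |
|---|---|---|
| 0.3 | 0.22 / 0.19 | 49% / 48% |
| 0.5 | 0.39 / 0.33 | 54% / 52% |
| 0.7 | 0.58 / 0.51 | 64% / 59% |

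For total bilirubin the range in these examples is about 48% to 64%, against 48% for the post-value t-test.

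**Change score**

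| r | Power at k = 0.5 / 1 / 2 | ANCOVA power |
|---|---|---|
| 0.3 | 50% / 36% / 16% | 51% |
| 0.5 | 59% / 48% / 20% | 59% |
| 0.7 | 73% / 69% / 25% | 75% |

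Example: at r = 0.5 and k = 2, v = 1 + 4 − 2 = 3 and the noncentrality is 0.5 / √(6/30) = 1.118, which gives 19.6%. At r = 0.5 and k = 0.5 the change score is fractionally ahead of ANCOVA (59.4% against 58.7%).

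**The case against.** The strongest reply is that this endpoint is not in the documents. The Protocol mentions bilirubin and liver function after drainage only as the basis for success rates, and no passage says that continuous values will be compared between arms. That stands: the point is conditional on reading the generic SAP rule as covering them.

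The gain is also uncertain and may be negligible. It is nil at r = 0.1 and small at r = 0.3. A reader might take 75% power as what adjustment would deliver, but for total bilirubin that is optimistic given the entry limit. The low power comes mainly from 30 per arm. This stands too, and keeps the severity low.

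It can be said that the form and timing are half settled: the Protocol speaks of a decrease and an improvement, the paired-test sentence speaks of changes, and surgery within 2 weeks bounds the sample. These words lean towards change, but nothing ties the Student's test to it or fixes a day.

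A reader might also infer that the unadjusted test is biased, because the title says "impact on pancreaticoduodenectomy: A prospective cohort study". The Methods section states random allocation, and under that statement the t-test is valid. The conflict between the two descriptions is a separate matter and is not used as support here.

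Finally, the multivariate sentence might be read as a planned adjusted analysis. It names no model, outcome or covariate, so it cannot be credited as one; it does need explaining.

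**Conclusion.** The point holds in a limited form, at low severity. The only usable between-arm method in the SAP for quantitative variables is an unadjusted Student's t-test. If it is applied to continuous bilirubin and liver tests, the pre-drainage values go unused. That these values precede drainage is itself inferred, from the order of the Methods section and from the bilirubin entry criterion.

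Under the stated random allocation the consequence is lost precision, not bias or an invalid test. Against 48% for the post-value t-test, the gain runs from none at r = 0.1 to 27 percentage points at r = 0.7. For total bilirubin the truncation examples put it between about 1 and 16 points. ANCOVA is level with or better than a change score to within a percentage point in every case computed, and far better if baseline values are much more spread out than post-drainage values. All of this rests on assumed values of r, k and the 0.5 SD difference.

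**What to change.** For each continuous liver test compared between arms, replace the Student's test with ANCOVA:

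- outcome: the last value after drainage and before pancreaticoduodenectomy;
- factor: drainage group;
- covariate: the last pre-drainage value of the same test;
- log scale if the values are skewed;
- report the adjusted difference, or ratio on the log scale, with a 95% CI.

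Keep the paired t-test as a within-arm description, labelled before and after drainage for these variables; its present label refers to surgery, whereas the Protocol judges drainage success after drainage. State what the multivariate sentence refers to, or delete it.

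The cost is SAP wording and one degree of freedom. The worst case, r = 0, is 1.8% more variance and power of 47.1% instead of 47.8%. The baseline is already collected and SPSS fits the model. One limit remains: the last pre-surgery sample can fall on different days in different patients, and ANCOVA on the baseline does not correct for unequal drainage duration.

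### The SAP's only within-patient test spans the operation, so it cannot show that a drainage method lowered bilirubin

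*SAP*

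**What the plan says.** The protocol's Methods section sets the drainage outcome: "For each method, the technical and clinical success rates will be observed by the improvement of liver functions and decrease in bilirubin after drainage". The next paragraph states: "Within 2 weeks, each patient in each group will undergo Pancreaticoduodenectomy (whipple operation) with triple anastomosis". Follow-up after that operation is described as "Patients will be closely observed in the immediate and early post-operative period for the occurrence of potential complications and mortality".

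The main aim, under Aim of the work, is a different outcome: "The aim of this prospective study is to compare postoperative complications in patients who will undergo pancreatoduodenectomy".

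For quantitative variables the SAP gives means and standard deviations, a Student's t test between the two drainage types, and one paired analysis: "Paired t test was used to compare between the pre and post-operative changes in the mean values of the quantitative variables". It defines no sampling times, does not list the quantitative variables, and describes no paired comparison across the drainage interval.

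**The concern.** The drainage effect that the protocol wants to observe lies between the drainage procedure and the operation. A pre- to post-operative pair does not cover that interval on its own. The operation removes the pancreatic head and reconstructs the biliary route, so it can be expected to lower bilirubin whatever the drain did. The documents do not say this outright; it is inferred from the nature of the resection.

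An analyst who follows the SAP literally could find a significant fall in each group and report that both methods worked, when some or all of the fall came from surgery.

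**Working it through.** The SAP gives no figure on this point, so there is none to reproduce. The check is one of wording, followed by an illustration of size.

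**1. What 'post-operative' refers to.** In the protocol's Methods, the intra-operative and post-operative observations both follow the sentence on the pancreaticoduodenectomy. The aim uses the word in the same sense. The drainage outcome is instead timed as after drainage. The natural reading of the SAP sentence is therefore after the pancreaticoduodenectomy.

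**2. What the pair measures.** Let T0 be the value before drainage, T1 the last value after drainage and before surgery, and T2 the post-operative value. Write D = T0 − T1 (fall from drainage) and S = T1 − T2 (fall from surgery).

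- If 'pre' is T0: T0 − T2 = D + S. The two parts cannot be separated.
- If 'pre' is T1: T1 − T2 = S. D does not enter.
- The protocol's outcome concerns D = T0 − T1, which the SAP does not pair.

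**3. Illustration when drainage does nothing (mean D = 0).**

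From the documents: 60 patients in two equal groups, so 60/2 = 30 per group; two-sided 0.05 level; entry criterion "high total bilirubin level more than 10 mg/dl".

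Assumed, because the documents give no values: mean S of 2, 5 or 8 mg/dl; D and S independent and normal, each with SD 3 or 5 mg/dl. There were 20,000 simulated runs per setting.

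For the T0–T2 pair the SD of the change is SD × √2, so the standardised mean is mean S ÷ (SD × √2 ÷ √30). For example:

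- Mean S = 2, SD 3: 2 ÷ (3 × 1.414 ÷ 5.477) = 2 ÷ 0.775 = 2.58
- Mean S = 2, SD 5: 2 ÷ 1.291 = 1.55
- Mean S = 5, SD 5: 5 ÷ 1.291 = 3.87

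Proportion of runs with p < 0.05:

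| Mean S (mg/dl) | SD | T0–T2 | T1–T2 | T0–T1 |
|---|---|---|---|---|
| 0 | 3 | 5% | 5% | 5% |
| 0 | 5 | 5% | 5% | 5% |
| 2 | 3 | 71% | 94% | 5% |
| 2 | 5 | 33% | 56% | 5% |
| 5 | 3 | 100% | 100% | 5% |
| 5 | 5 | 96% | 100% | 5% |
| 8 | 3 | 100% | 100% | 5% |
| 8 | 5 | 100% | 100% | 5% |

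Only the T0–T1 pair keeps its nominal level as a test of drainage throughout. The other two keep it only if surgery has no effect on bilirubin by the time of the post-operative sample.

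**The case against.** Several counter-arguments have force.

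- **The drainage outcome is not untested.** A success rate is a proportion, and the SAP covers proportions with chi-squared, Monte Carlo or Fisher tests by drainage type. Post-drainage bilirubin can go through Student's t test. The protocol does not explicitly ask for a within-patient significance test. This stands: those between-group tests are not wrong in themselves. But they state no time point, and they do not supply a paired comparison over the drainage interval.
- **The paired sentence does not name bilirubin**, and a pre- to post-operative comparison can properly describe recovery after surgery. This also stands. The difficulty arises if the result is read as evidence on drainage, and the SAP has no other paired analysis that could serve that purpose.
- **'Post-operative' may be loose wording for 'after the drainage procedure'**, since ERCP is done under general anaesthesia. This is possible, but the protocol's own usage points the other way. If it was meant, the sentence still needs rewording.
- **The percentages rest on assumed inputs**, and the surgical fall depends on when post-operative blood is taken, which is not stated. This is correct.

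Two stronger readings are tempting. A reader might infer that the paired test will be significant in both groups even if drainage did nothing. The documents give no bilirubin changes to support that certainty, and with a small surgical fall it happened in only 33–71% of runs. A reader might also infer that the test could hide or reverse a difference between the methods. That would require comparing the pre- to post-operative changes across groups. The SAP does not say this is done: the paired test works within patients, and the comparison of drainage types is assigned to Student's t test.

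**Conclusion.** The concern holds in a limited form. With 'post-operative' read as the protocol uses it, the SAP's only within-patient test either mixes drainage with surgery or leaves drainage out. It cannot show that a drainage method lowered bilirubin. That conclusion rests on the text and needs no assumed figure.

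The size does depend on assumptions. With no drainage effect, false support for drainage from the pre-drainage to post-operative test ranges from about a third of runs (surgical fall 2 mg/dl, SD 5) to practically all (fall of 5 mg/dl or more), against about 5% for the pre- to post-drainage pair.

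The consequence is confined to a supporting outcome. The main aim, postoperative complications, is untouched. Severity: should-fix.

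**What to change.** Define three times in the SAP: T0, before drainage; T1, the last value after drainage and before pancreaticoduodenectomy; T2, post-operative. Then:

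- Run the within-group paired tests of bilirubin and liver function on T0 and T1, and derive clinical success from the same pair.
- Compare the groups on T1 adjusted for T0 by ANCOVA. Two within-group paired tests cannot show which method lowers bilirubin more.
- Report T2 separately as recovery after surgery, and not as evidence on drainage.

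The cost is mainly SAP wording. The protocol already observes bilirubin and liver function after drainage, so no new type of measurement is needed. The one practical demand is that a T1 value be identified for each patient. The protocol sets no sampling schedule for it, so the SAP should say which recorded measurement counts as T1.
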